6.2 Efficacy Analyses

6.2.1 Primary Efficacy Analysis

CSF Biomarkers

The baseline, post baseline, and change from baseline values will be summarized by treatment group based on the FAS population. The change from baseline on Day 28 will be analyzed by using a General Linear Model for the ANCOVA. The model will include the change from baseline as the dependent variable, the fixed effect of treatments, and baseline CSF biomarkers measurement as covariate. The means, Least Squares (LS) means, a 2 sided 95% confidence intervals (CI) for each LS means, differences between LS means, a 2 sided 95% CIs for each difference and the p-values from model effects will be reported in the summary table.

6.2.2 Secondary Efficacy Analysis

CSF Biomarkers at Screening Visit 2 and Day 28 will be compared by using the two tailed paired t-test per each treatment group (Placebo, PTI-125 50 mg, and PTI-125 100 mg). The analysis will be performed based on the FAS population. The means, differences between means of Screening Visit 2 and Day 28, a 2 sided 95% CIs for the difference and the p-values from the t-test will be reported in the summary table.

Cambridge Cognition Test

Results will be summarized for subjects by treatment group. The summary and statistical analysis will be conducted using FAS population. The change from baseline on Day 28 will be analyzed by using a General Linear Model for the ANCOVA. The model will include the change from baseline as the dependent variable, the fixed effect of treatments, and baseline Cambridge cognition measurement as covariate. The means, Least Squares (LS) means, a 2 sided 95% confidence intervals (CI) for each LS means, differences between LS means, a 2 sided 95% CIs for each difference and the p-values from model effects will be reported in the summary table.

Dose Response Analysis 6.2.3

Nonlinear Emax model will be used in dose-response analysis. The model has the following form:

$$R_i = E_0 + \frac{D_i^N \times E_{max}}{D_i^N + ED_{50}^N} + \varepsilon_i$$

Where:

i = patient;

 R_i = The value of response for patient i (ex. Defined to be "Change form Baseline in A β_{42} at Day 28" should be repeated for the remaining CSF Biomarkers);

 D_i = Concentration of the drug in the plasma of the patient *i* at Day 28;

 E_0 = Basal response, when the concentration of the drug is zero or minimal;

 E_{max} = The maximum response attributable to the drug;

ED₅₀ = The concentration that produces half of maximum response;

N = The slope measures the change in response by moving from one concentration level to another;

 ε_i = The random error term for patient *i* – i.i.d and follows normal distribution with mean – 0 and variance.

Treatment group response will be predicted by applying the Emax model which intrinsically has 4 parameters to estimate (E0, Emax, ED50, N). This can be performed with "Proc NLIN" procedure in SAS by arbitrary specifying starting estimates for these parameters by treatment groups.

To assure optimal convergence of the procedure, the following starting estimates will be applied:

	Placebo	PTI-125 50mg	PTI-125 100mg
E ₀	0	Minimum response from observed data	Minimum response from observed data
E _{max}	100	Maximum response from observed data	Maximum response from observed data
ED ₅₀	5	1	1
N	1	1	1

Results will be summarized and presented graphically by treatment groups based on the FAS. Parameter estimates will be presented together with 95% Cls.

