1.2.4 PK Endpoint

The PK endpoint for this study is the C_{min} value from the blood samples taken on Days 7, 14 and 28. CSF to plasma ratio will be determined using the Day 28 CSF and plasma samples.

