2.0 Background

2.1 Study Design

This Phase 2b study is a randomized, double-blind, placebo-controlled trial of PTI-125 oral tablets given to patients with mild to moderate Alzheimer's Disease. Sixty patients are expected to be enrolled in the trial and randomized to one of the three cohorts. Cohorts will receive placebo or PTI-125 at 50 or 100 mg twice a day.

Two screening visits will be scheduled within 30 days of start of the study (Figure 1) Subjects meeting the initial screening criteria will return for a cerebrospinal fluid (CSF) draw at a second screening visit. A second CSF sample will be collected at day 28 visit for CSF biomarkers as well as analysis of PTI-125. Cambridge Cognition testing will be conducted at the second Screening visit, Day 1 and at the Day 28 visit.

On Screening visit 1 and Day 28, patients will be assessed for suicidality via the C-SSRS.

Subjects will report to the clinic on the morning of Day 1 and the following will be conducted: Cambridge Cognition testing, a full physical exam, an ECG and a blood draw for clinical labs and biomarkers. Subjects will be monitored for Adverse Events (AE) and Vital Signs (VS) will be taken through 2 hours post- dosing. Subjects will return to the clinic on Days 7, 14 and 28 for blood draws for clinical laboratory testing, safety assessments of vital signs, ECGs.

PK blood samples will be obtained prior to the first dose on Day 7, Day 14, and Day 28 for C_{min} values. On Day 28, there will be a CSF draw after the last dose, and an additional PK blood sample will be obtained after this CSF draw for calculation of CSF/plasma ratio.

Blood samples for testing in PTI-125Dx, the companion diagnostic/biomarker, mTOR activation and other potential blood-based biomarkers will be drawn on Day 1 and Day 28. The Day 14 blood sample will also be used for APOE genotyping. A CSF sample collection will be performed on Day 28 for neurogranin, neurofilament light chain, total tau, pTau (T181), A β 42, A β 40, YKL40, IL-6, IL-1 β , TNF α and other potential CSF biomarker assays as well as bioanalysis of PTI-125.

Figure 1. Study Design Schema

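### SAP 6.2.3 does not say whether the Emax dose-response model is fitted to all arms together or separately by arm; run by arm, placebo yields only E0 and an active arm cannot usefully estimate ED50

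*SAP*

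**What the plan says.** Dose-response is the third objective (SAP 1.1) and a secondary endpoint (SAP 1.2.2). SAP 6.2.3 is the only analysis that carries that label. It gives a single Emax equation for patient i, with parameters E0, Emax, ED50 and N and no arm index. The regressor D_i is defined as "Concentration of the drug in the plasma of the patient" at Day 28, with no unit. E0 is defined as "Basal response, when the concentration of the drug is zero or minimal".

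The section continues: "Treatment group response will be predicted by applying the Emax model which intrinsically has 4 parameters to estimate". The model is to be run in Proc NLIN "by arbitrary specifying starting estimates for these parameters by treatment groups". The table of starting values has three columns (E0 / Emax / ED50 / N):

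- Placebo: 0 / 100 / 5 / 1.
- 50 mg and 100 mg, each: observed minimum / observed maximum / 1 / 1.

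On output it says "Results will be summarized and presented graphically by treatment groups based on the FAS", and "Parameter estimates will be presented together with 95"% confidence intervals.

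The documents differ on the Day 28 sample. SAP 1.2.4 takes the Cmin "value from the blood samples taken on Days 7, 14 and 28". SAP 2.1 says "PK blood samples will be obtained prior to the first dose on Day 7, Day 14, and Day 28" and adds a further sample after the CSF draw. Protocol 7.2.6 has the patient dose on arrival on Day 28, and Protocol 7.2.6 and 10.3 provide only the sample after the CSF draw.

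**The concern.** The arm-specific starting values and the by-group reporting point to one fit per arm. The unsubscripted equation and the definition of E0 point to one fit that includes placebo. Two competent programmers could follow the same text and run different analyses.

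The choice matters because an Emax curve needs a zero anchor and a spread of exposure. Placebo has no exposure, and each active arm clusters around one exposure level with no zero. If the by-arm reading were followed, the only analysis labelled dose-response would promise intervals that cannot be computed in placebo, and would give active-arm ED50 values that carry almost no information. The missing unit and the unreconciled Day 28 sample leave the regressor itself open.

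**Working it through.** **The plan's own figure.** There is none to reproduce for this model. The sample size is 3 × 20 = 60, and neither document gives a power, effect size or SD.

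**Step 1: placebo alone (exact, given D=0).** Write Z = D^N/(D^N + ED50^N). The derivatives of the mean response are:

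- for E0: 1
- for Emax: Z
- for log ED50: −Emax·N·Z(1−Z)
- for N: Emax·Z(1−Z)·ln(D/ED50)

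At D=0, Z=0 and the last three vanish for every patient. The Jacobian has rank 1 of 4, so only E0 is estimable.

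**Step 2: inputs for the active arms.**

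- From the documents: n=20 per arm (Protocol 4). Mean Day 28 exposure at 100 mg b.i.d. is Cmax 1,104 ng/mL and AUC 8,483 h·ng/mL (Protocol 2, Tables 1–4). PK was dose-proportional in the first-in-human study (Protocol 2).
- Derived exposure settings: 552/1,104 ng/mL (half of Cmax, and Cmax), and 177/353 ng/mL (8,483/24 = 353, and half of it).
- Assumed, because the documents do not give them: lognormal concentrations with CV 25, 35, 50 or 60%; true ED50 200, 400 or 800 ng/mL; true N=1; independent normal errors. This makes 4 × 3 = 12 scenarios per exposure setting.

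**Step 3: precision of ED50.** SE(log ED50), which equals SE(ED50)/ED50 by the delta method, is the square root of the log ED50 diagonal element of SD²·(J′J)⁻¹. It is proportional to SD/|Emax|, so ratios between fits depend on neither SD nor Emax. At SD/|Emax| = 0.125 and means 552/1,104:

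| Fit | N free | N=1 |
|---|---|---|
| Better active arm | at least 1.85 | at least 1.52 |
| Three arms pooled | 0.30–2.0 | 0.27–0.43 |

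At 177/353 the per-arm ratio is also at least 1.5, and pooled N=1 gives 0.30–1.17.

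Like-for-like factor, taken scenario by scenario (smaller of the two per-arm SEs divided by the pooled SE):

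| Arm means (ng/mL) | N free in both | N=1 in both |
|---|---|---|
| 552/1,104 | 2.1–248 | 4.6–27 |
| 177/353 | 1.8–11 | 2.8–17 |

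**Step 4: does the 95% CI for ED50 exclude zero?** It does when SE/ED50 is below 1/1.96 = 0.51.

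- Per arm at 0.125: the minimum is about 1.5, so 0 of 12 in both exposure settings.
- Pooled N=1 at 0.125: 12 of 12 (552/1,104) and 6 of 12 (177/353).
- Pooled N=1 at 0.25: the smallest values double, 0.27 × 2 = 0.54 and 0.30 × 2 = 0.60. Both exceed 0.51, so none.
- Pooled with N free: adding a parameter cannot lower the SE, so the interval is never narrower than with N=1.

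**Step 5: simulation (Emax 2 residual SDs, CV 40%, means 552/1,104, 60 runs per setting, several starting points).** True ED50 was 200, 552 or 2,000.

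- Per arm, four parameters: median ED50 was 467–606 in the 50 mg arm and 882–1,162 in the 100 mg arm, whichever value was true. N ran to its bound in 53–60% of fits. The fit returns roughly the arm's own mean concentration.
- Per arm, N=1: within two-fold of the truth in 2–10%.
- Pooled, N=1: within two-fold in 42, 48 and 18%.
- Pooled, N free: within two-fold in 37, 53 and 28%, with N at its bound in 15–30%.

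The Monte Carlo SE of a proportion near 50% is √(0.25/60) = 6.5 points, so the two pooled variants are not clearly separated.

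**Step 6: linear slope.** In simulations with Emax of 1 and 2 residual SDs, the pooled slope was detected in about 49% and 98% of runs, against 9–14% within one active arm.

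**Step 7: bias from fixing N=1.** In noise-free pooled fits at 552/1,104, a true N of 2 puts ED50 at 0.67–7.0 times its value, and a true N of 0.5 at 0.29–0.75 times. At 177/353 with true N=2, the result runs from 2.4 times the truth to no usable ED50 in 6 of 12 scenarios. With true N=0.5 it is 0.14–0.37 times.

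**The case against.** The strongest reply is that per-arm fitting is an inference. One equation without arm subscripts, a baseline defined at zero concentration, predicted group responses and results shown by group are all compatible with a single pooled model. This stands: a reader might infer that the SAP prescribes three separate fits, but no sentence says so. What remains is an ambiguity, one reading of which gives unusable output.

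Four further inferences are tempting and not supported.

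- That ED50 is not identifiable within an active arm. D_i is individual concentration and varies between patients, so the information matrix is not singular. The problem is precision.
- That a pooled fit cannot use three starting vectors. It can be run from each, keeping the smallest residual sum of squares. The starting values are a convergence matter with no shown effect on results.
- That the gain from pooling is 5.6 to 248-fold. That range compares a four-parameter per-arm fit with a pooled N=1 fit and so mixes two changes.
- That N=1 is the better model. Steps 5 and 7 do not show it.

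It is also fair to say that the consequence is limited. SAP 1.3 and 6.2.1 already compare the randomised arms with intervals, and those comparisons carry the main dose-response evidence. This limits the weight of the point, but does not settle what 6.2.3 tells the programmer to do.

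**Conclusion.** The point holds as an ambiguity that should be resolved before unblinding. The placebo result is exact given zero concentration: on the by-arm reading three of the four promised placebo intervals cannot exist. The active-arm result is conditional on the assumed concentrations, CVs, ED50 values and true N=1. Within that range no per-arm ED50 interval excluded zero, even at SD/|Emax| = 0.125.

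Pooling is clearly better but does not make ED50 reliable. With N=1 the interval excludes zero in none of the scenarios once SD/|Emax| reaches 0.25, and no document gives an SD or Emax from which to judge where this trial lies. A reader should not conclude that the dose-response objective is lost or that the primary analysis is affected: the ANCOVA on randomised dose does not depend on this model.

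**What to change.** Amend SAP 6.2.3 before unblinding:

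1. For each CSF biomarker, fit one Emax model to all FAS patients of the three arms together, with one common parameter set. Placebo is the zero-concentration anchor, checked against the placebo assay of Protocol 7.3.3. Several starting vectors may be tried, keeping the fit with the smallest residual sum of squares.
2. Always report the pooled linear concentration slope with its 95% CI beside the Emax fit.
3. Do not interpret ED50 if its 95% CI includes zero.
4. Prespecify the role of N=1, either as a reduced model or as the fallback when free N does not converge or reaches its bound. State that it biases ED50 if the true N is not 1.
5. State the concentration unit. Name the Day 28 plasma sample used as D_i after reconciling SAP 1.2.4 and 2.1 with Protocol 7.2.6 and 10.3.
6. Keep dose-response as a secondary endpoint, or amend SAP 1.2.2 openly if it is to be called exploratory. Note that the ANCOVA comparisons in 6.2.1 are the main dose-response evidence, because concentration within an arm is not randomised.

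The cost is SAP wording and modest programming, with no new data. The downside is that for many biomarkers the rule in item 3 may leave no ED50 to interpret.

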1.1 Study Objectives

Live v1.2 12Feb2020

The primary objectives for this study are to:

- Assess the safety of PTI-125 following 1-month, repeat-dose oral administration in mild-to-moderate Alzheimer's Disease (AD) patients, 50-85 years of age, with 16 ≤ MMSE ≤ 26.
- Assess the effect on biomarkers of PTI-125 following 1-month, repeat-dose oral administration in mild-tomoderate AD patients, 50-85 years of age, with 16 ≤ MMSE ≤ 26.
- Assess the effect on cognition of PTI-125 following 1-month, repeat-dose oral administration in mild-tomoderate AD patients, 50-85 years of age, with 16 ≤ MMSE ≤ 26.

The second objective is to replicate the effects on biomarker shown in the previous open label 1-month study.

The third objective is to investigate a dose response of PTI-125.

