1.2.2 Secondary Endpoint

- The secondary endpoint for this study will be to evaluate the change in CSF biomarkers from the second screening to Day 28 within the study treatment groups.
- The secondary endpoint for this study will be to evaluate the change in Cambridge Cognition testing from the Day 1 to Day 28 between each dose group and placebo
- ٩
- The secondary endpoint for this study will be the dose-response of the study drug.

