4.2. Covariates and Subgroups

4.2.1. Planned Covariates

Covariates for analysis of key efficacy data will be identified prior to study unblinding

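### The SAP's Emax dose-response model leaves out the baseline biomarker that its ANCOVA uses for the same CSF change, so the dose-response estimates are modestly less precise than they need be

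*SAP*

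**What the plan says.** The primary CSF analysis in SAP 6.2.1 is an ANCOVA of change to Day 28: "The model will include the change from baseline as the dependent variable, the fixed effect of treatments, and baseline CSF biomarkers measurement as covariate". The Cambridge Cognition ANCOVA in SAP 6.2.2 also adjusts for its own baseline.

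SAP 6.2.3 takes the same response, defined as "The value of response for patient i", with change from baseline in Aβ42 as the example and the other CSF biomarkers to follow. The regressor is "Concentration of the drug in the plasma of the patient" at Day 28. The written equation contains E0, Emax, ED50, N and an error term, and the text confirms the count: "Treatment group response will be predicted by applying the Emax model which intrinsically has 4 parameters to estimate (E0, Emax, ED50, N"). No baseline term appears in the equation, the definitions or the table of starting values. That table has a separate column for each treatment group.

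On status, SAP 1.1 says "The third objective is to investigate a dose response of PTI-125", and SAP 1.2.2 says "The secondary endpoint for this study will be the dose-response of the study drug". SAP 6.2.3 plans parameter estimates with 95% confidence intervals and plots by treatment group. It specifies no dose-response hypothesis test.

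SAP 4.2.1 adds only that "Covariates for analysis of key efficacy data will be identified prior to study unblinding".

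**The concern.** A change score removes the baseline fully only if Day 28 values rise one for one with baseline. Usually they do not: patients with a high first reading tend to fall and those with a low one tend to rise, through regression to the mean and assay error at baseline. Without a baseline term, that part of the change stays in the residual and widens the intervals for the dose-response curve.

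With about 20 patients per arm, the arms will also differ somewhat in baseline by chance. In one fit across all arms, placebo patients sit at zero concentration and the 100 mg patients at the high end, so a chance baseline difference between arms can look like part of an exposure effect. The ANCOVA results shown beside the curve would be adjusted for that difference, and the curve would not. The plan gives no reason for treating the two analyses differently.

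**Working it through.** **Inputs.** From the documents: 60 patients randomised 1:1:1, so 60/3 = 20 per arm (SAP 2.3.1, 2.7), and a mean Day 28 Cmax of 1,104 ng/mL at 100 mg b.i.d. in the earlier patient study (protocol Table 1). The plan states no precision or power for the dose-response analysis, so there is no figure to reproduce. Assumed: equal SD s at both visits and a baseline/Day 28 correlation ρ of 0.5, 0.7 or 0.9. The documents give neither an SD nor ρ.

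**Step 1: what the baseline term removes.**
- Variance of change: 2s²(1 − ρ).
- Slope of change on baseline: (ρs² − s²)/s² = −(1 − ρ). It is not zero unless ρ = 1.
- Residual variance after adjustment: 2s²(1 − ρ) − (1 − ρ)²s² = s²(1 − ρ²).
- Ratio, adjusted to unadjusted: (1 + ρ)/2 = 0.75, 0.85, 0.95.
- SE ratio: √0.75 = 0.87, √0.85 = 0.92, √0.95 = 0.97.

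This is a linear-model benchmark. The planned model is nonlinear, so it was also simulated.

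**Step 2: the Emax model itself.** Trials of 20 per arm were simulated and all arms fitted together, with and without a centred baseline term. Run A: N fixed at 1, 1,500 trials per ρ, concentrations of 0, median 552 (half of 1,104) and median 1,104 ng/mL with log-SD 0.4, true ED50 500, prediction at 1,000 ng/mL. Run B: N fixed at 1, 600 trials per ρ, log-SD 0.35, ED50 at the typical low-dose concentration, prediction at the typical high-dose concentration. Two further runs at 1,000 ng/mL estimated N, as the SAP plans. Apart from the 1,104 ng/mL, these settings are assumptions.

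Reduction in the SD of the predicted effect when baseline is added:

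| ρ | Linear benchmark | Run A | Run B | N estimated (two runs) |
|---|---|---|---|---|
| 0.5 | 13% | 11% | 13% | 11% and 12% |
| 0.7 | 8% | 6% | 7% | 5% and 8% |
| 0.9 | 3% | 1% | 3% | none and 1% |

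A further pooled run with N fixed at 1 gave 11%, 6% and 3%. A fair summary is about 11%, 6% and 1 to 3%, with the other settings within two percentage points.

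**Step 3: chance imbalance, if the arms are pooled.** The baseline difference between two arms of 20 has SD √(2/20) = 0.32 baseline SD, and exceeds 0.5 SD in either direction with probability 2 × [1 − Φ(0.5/0.316)] = 11%. A 0.5 SD imbalance shifts the unadjusted difference in change by 0.5 × (1 − ρ) = 0.25, 0.15 and 0.05 baseline SD.

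**Step 4: validity.** In a linear comparison of 100 mg with placebo under no effect (20,000 trials per ρ), rejection at the 5% level was 5.1%, 4.9% and 5.0% unadjusted, and 4.8%, 5.0% and 5.0% adjusted. Leaving baseline out does not inflate type I error.

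**Step 5: what baseline does not repair.** With N fixed at 1, about 18 to 23% of fits ran to an ED50 bound, with or without baseline. With N free over a grid, N reached a grid limit in about 55 to 65% of fits either way. Freeing N raised the SD by about 15 to 25%, as much as or more than omitting baseline did.

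**The case against.** *SAP 4.2.1 may already cover it.* It leaves room to add covariates before unblinding, and that is a useful route. But it names none, does not mention the Emax model, and leaves a fully written four-parameter equation as it stands.

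*An Emax model without covariates is legitimate, and this one is limited mainly by weak identification.* Both parts stand. They keep the point modest; they do not justify leaving removable noise in the residual.

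*The imbalance argument assumes a pooled fit.* This also stands. Starting values by treatment group leave it open whether one curve or three are fitted. If each arm is fitted alone, between-arm baseline differences cannot enter the within-arm exposure effect, though the lost precision remains. A separate placebo fit would have no concentration range from which to estimate Emax, ED50 or N, so the SAP should say which is meant.

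Three stronger readings are tempting, and the documents do not support them:

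- *That the curve and the ANCOVA could disagree for an arm solely because one is adjusted.* They also differ because the Emax regressor is measured Day 28 plasma concentration and the ANCOVA uses the arm. Adjustment removes one source of difference, not all.
- *That the dose-response analysis loses a stated amount of power.* No dose-response test is planned, so power for a linear slope or an arm contrast does not describe this analysis. The SD of the predicted effect does.
- *That the unadjusted model is biased.* Between randomised arms, baseline differences arise by chance. Within the active arms concentration is not randomised, so baseline could be related to it in a non-random way, but nothing in the documents shows that it is.

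**Conclusion.** The omission is a matter of fact: the same response is adjusted for baseline in SAP 6.2.1 and not in 6.2.3, without explanation. The dose-response estimates are therefore less precise than they need be, and in a pooled fit they also carry chance baseline differences between arms.

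The size is modest and rests on the assumed correlation, equal variances and a pooled fit: an SD of the predicted effect about 11% smaller at 0.5, 6% at 0.7 and 1 to 3% at 0.9. The benefit would vanish if change were unrelated to baseline. The analysis is secondary and planned as estimation, so this is an improvement worth making because it is nearly free. It is not a flaw that invalidates the analysis.

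**What to change.** Before unblinding, amend SAP 6.2.3 as follows:

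- Add one linear term to the equation: R_i = E0 + β × (baseline_i − mean baseline) + the existing drug term + error. Use the Screening Visit 2 value of the same biomarker, the baseline from which SAP Table 2 calculates the change.
- State that the model is fitted to all three arms together.
- Report predicted responses at the mean baseline.
- Carry the same covariate into any simpler concentration or dose model used if the Emax fit fails.

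If the sponsor prefers to leave baseline out, the SAP should say why. SAP 3.0 already requires Screening 2 and Day 28 data for the biomarker analysis, so nothing new is collected. The cost is one sentence and one degree of freedom. Identification of ED50 and N needs separate attention.
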